3.4 Randomization and Blinding

Prior to randomization, participants completed baseline data collection and received the healthy food prescription. Researchers randomized participants to either the FoodRx (n=299) or comparison (n=297) group with a 1:1 allocation ratio using a computer-generated, concealed, blocked randomization sequence in REDCap (Research Electronic Data Capture)⁴¹ created by an independent statistician. Blocking variables included gender identity (woman, man), recruitment location (urban setting, rural setting, Indigenous primary care clinic), and baseline A1C (6.5-8.5%, 8.6-12%). The intervention group received both a healthy food prescription and a healthy food incentive. The comparison group received a healthy food prescription alone.

Due to the nature of the intervention, participants were not blinded to their allocation; however, they were blinded to study objectives. Participants in the comparison group were also blinded to the details of the healthy food incentive, including its monetary value and eligible foods. Care providers and researchers who collected and analyzed the data were blinded to treatment allocation with the exception of a research assistant who assisted participants in the intervention group throughout the trial.

4. Trial Population

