4.3 Stopping Guidance and Interim Analysis

The FoodRx program was deemed a low risk to cause adverse events; thus, no stopping guidance was required, and no interim analyses were planned or conducted. Participants continued their regular care with their primary care physician and/or other care providers during the trial, including adjustments to medication regimes to improve glycemia at the providers discretion. At the conclusion of the study, participants continued to be followed by their care providers.

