6.3 Analysis Population

Analyses will be intention-to-treat using all available data for parameter estimation of primary, secondary, and exploratory outcomes.

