Systolic Blood Pressure We will assess group differences in systolic blood pressure as a continuous outcome using mixed-effects linear regression. Models will be adjusted for baseline systolic blood pressure, and blocking variables (baseline A1C, gender, recruitment location). To improve the precision of effect estimates, models will also be adjusted for age, race/ethnicity, educational attainment, number of children living in the home, and diabetes duration. Additionally, all models will include baseline A1C data source (study measured vs administrative health data), and group (FoodRx vs comparison) indicator variables. We will include random intercepts for participants (participant study ID) to account for within-subject correlation due to repeated measures, and for primary care clinics (clinic study ID) to account for clustering of participants within clinics.

In addition to per-protocol and as-treated analyses, we will conduct sensitivity analyses for systolic blood pressure to examine impact of excluding patients who were started on anti-hypertensive therapy.

Diastolic Blood Pressure We will assess group differences in diastolic blood pressure as a continuous outcome using mixed-effects linear regression. Models will be adjusted for baseline diastolic blood pressure, and blocking variables (baseline A1C, gender, recruitment location). To improve the precision of effect estimates, models will also be adjusted for age, race/ethnicity, educational attainment, number of children living in the home, and diabetes duration. Additionally, all models will include baseline A1C data source (study measured vs administrative health data), and group (FoodRx vs comparison) indicator variables. We will include random intercepts for participants (participant study ID) to account for within-subject correlation due to repeated measures, and for primary care clinics (clinic study ID) to account for clustering of participants within clinics.

In addition to per-protocol and as-treated analyses, we will conduct sensitivity analyses for diastolic blood pressure to examine impact of excluding patients who were started on anti-hypertensive therapy.

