Lipids – Apolipoprotein B We will assess group differences in Apo B as a continuous outcome using mixed-effects linear regression. Models will be adjusted for baseline Apo B, and blocking variables (baseline A1C, gender, recruitment location). To improve the precision of effect estimates, models will also be adjusted for age, race/ethnicity, educational attainment, number of children living in the home, and diabetes duration. Additionally, all models will include baseline A1C data source (study measured vs administrative health data), and group (FoodRx vs comparison) indicator variables. We will include random intercepts for participants (participant study ID) to account for within-subject correlation due to repeated measures, and for primary care clinics (clinic study ID) to account for clustering of participants within clinics.

In addition to per-protocol and as-treated analyses, we will conduct sensitivity analyses for Apo B to examine the impact of excluding patients who were started on lipid-lowering therapy.

Lipids – Triglycerides We will assess group differences in triglycerides as a continuous outcome using mixed-effects linear regression. Models will be adjusted for baseline triglycerides, and blocking variables (baseline A1C, gender, recruitment location). To improve the precision of effect estimates, models will also be adjusted for age, race/ethnicity, educational attainment, number of children living in the home, and diabetes duration. Additionally, all models will include baseline A1C data source (study measured vs administrative health data), and group (FoodRx vs comparison) indicator variables. We will include random intercepts for participants

(participant study ID) to account for within-subject correlation due to repeated measures, and for primary care clinics (clinic study ID) to account for clustering of participants within clinics.

In addition to per-protocol and as-treated analyses, we will conduct sensitivity analyses for triglycerides to examine the impact of excluding patients who were started on lipid-lowering therapy.

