Lipids – HDL We will assess group differences in HDL as a continuous outcome using mixed-effects linear regression. Models will be adjusted for baseline HDL, and blocking variables (baseline A1C, gender, recruitment location). To improve the precision of effect estimates, models will also be adjusted for age, race/ethnicity, educational attainment, number of children living in the home, and diabetes duration. Additionally, all models will include baseline A1C data source (study measured vs administrative health data), and group (FoodRx vs comparison) indicator variables. We will include random intercepts for participants (participant study ID) to account for within-subject correlation due to repeated measures, and for primary care clinics (clinic study ID) to account for clustering of participants within clinics.

In addition to per-protocol and as-treated analyses, we will conduct sensitivity analyses for HDL to examine the impact of excluding patients who were started on lipid-lowering therapy.

BMI We will assess group differences in BMI as a continuous outcome using mixed-effects linear regression. Models will be adjusted for baseline BMI, and blocking variables (baseline A1C, gender, recruitment location). To improve the precision of effect estimates, models will also be adjusted for age, race/ethnicity, educational attainment, number of children living in the home, and diabetes duration. Additionally, all models will include baseline A1C data source (study measured vs administrative health data), and group (FoodRx vs comparison) indicator variables. We will include random intercepts for participants (participant study ID) to account for within-subject correlation due to repeated measures, and for primary care clinics (clinic study ID) to account for clustering of participants within clinics.

In addition to per-protocol and as-treated analyses, we will conduct sensitivity analyses for BMI to examine the impact of BMI as an ordinal outcome (underweight/healthy weight, overweight, obese) using logistic regression models.

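### The blood pressure and lipid sensitivity analyses drop participants who started a drug during follow-up; the likely bias is small, but the comparison is no longer randomised and is a weak test of robustness

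*SAP*

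**What the plan says.** Section 6.3 sets the population: "Analyses will be intention-to-treat using all available data for parameter estimation of primary, secondary, and exploratory outcomes". Section 7.4 then gives each marker a main mixed model and, besides the per-protocol and as-treated analyses, one marker-specific sensitivity analysis on concomitant drugs. For systolic and diastolic pressure it looks at the "impact of excluding patients who were started on anti-hypertensive therapy". For Apo B, triglycerides and HDL it looks at "the impact of excluding patients who were started on lipid-lowering therapy".

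The SAP gives no time window for a start, no data source for these two drug classes, and no statement of how a result that differs from the main analysis will be read. Section 4.3 shows that drug changes could occur on study: "Participants continued their regular care with their primary care physician and/or other care providers during the trial, including adjustments to medication regimes". Section 3.4 says that "participants were not blinded to their allocation", while care providers were blinded.

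For 12-month A1C, the corresponding sensitivity analysis in section 7.4 adjusts for changes in drug type and dosage, and so keeps the participants.

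**The concern.** A drug start during follow-up happens after randomisation. If prescribing responds to measured pressure or lipids, those who start are mostly those with high values. If FoodRx improves the marker, fewer people start in that arm, even with blinded prescribers. Removing starters then takes more high values out of the comparison arm and narrows the contrast. If starting differs between arms for some other reason, a difference can appear where there is none.

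The rule also removes whole participants. Someone measured at 6 months who starts a drug later loses a 6-month value that the drug never touched.

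At stake is the reading of the result. The natural use of this analysis is to say that the finding does not depend on added drugs, and a comparison selected in this way supports that statement poorly.

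**Working it through.** The SAP states no figure for these analyses, so there is none to reproduce. The check is an illustration of the mechanism for systolic pressure only.

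**Inputs from the SAP.** 299 + 297 = 596 randomised (section 3.4); 30% attrition (section 4.2).

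**Assumed inputs.** Mean 135 mmHg, SD 15, correlation 0.6 between visits, and a drug effect of -10 mmHg. Starts fall between months 6 and 12, with logit P(start) = a + 0.15 × (6-month pressure - 135), where a is set so that 10%, 20% or 30% of the comparison arm start. Each scenario has 1,000,000 simulated participants and is analysed by regression on arm and baseline.

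**True effect -5 mmHg, estimates at 12 months:**

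| Start, comparison | Start, FoodRx | All, as measured | Starters excluded | Shortfall of exclusion |
|---|---|---|---|---|
| 10% | 6% | -4.62 | -4.80 | 0.20 |
| 20% | 13% | -4.35 | -4.70 | 0.30 |
| 30% | 22% | -4.17 | -4.64 | 0.36 |

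Share of the masked effect that exclusion recovers:
- (4.80 - 4.62)/(5 - 4.62) = 47%
- (4.70 - 4.35)/(5 - 4.35) = 54%
- (4.64 - 4.17)/(5 - 4.17) = 57%

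Starters' 6-month pressure averages about 20 to 24 mmHg above that of non-starters.

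**No true effect, 12 months.** With equal start rates, exclusion is unbiased (within 0.06, which is simulation noise). With start odds about doubled in FoodRx it gives -0.22, -0.38 and -0.43; with odds about halved, +0.18, +0.30 and +0.35. The as-measured estimates move further: -0.48 to -0.90 and +0.36 to +0.77.

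**6 months.** Nobody has yet taken the drug, so the analysis of all participants is unbiased at -5. With a milder start rule (starters 15 to 20 mmHg above non-starters), exclusion gives -4.1 to -4.7. With the steeper rule of the table it gives -3.9 to -4.5. With no true effect and unequal start odds, the spurious difference is 0.8 to 1.0 mmHg under the milder rule and 0.5 to 1.2 under the steeper one.

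**Post-start values set to missing, earlier values kept.** At 12 months this returns about -5 when the true effect is -5, and about 0 when there is none. If the start precedes the first follow-up measurement, the participant contributes no outcome either way, and this analysis equals exclusion.

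**Scale.** Residual SD = 15 × √(1 - 0.6²) = 12. Standard error = 12 × √(1/299 + 1/297) = 0.98 mmHg, or 0.98/√0.7 = 1.17 after 30% attrition. The 12-month shortfall of 0.20 to 0.36 is thus about a fifth to a third of a standard error. In the 20% row about (19.8 + 13.4)/2 = 16.6% of participants are lost, which alone widens the standard error by 1/√0.834 = 1.10.

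**The case against.** The case for leaving the plan alone is substantial.

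- These are labelled sensitivity analyses of secondary outcomes. A reader might infer a conflict with the intention-to-treat rule in section 6.3. There is none, because the main analyses keep everyone.
- A reader might infer that exclusion makes matters worse than the main analysis, or recovers almost none of the masked effect. At 12 months the illustration shows the opposite: exclusion is closer to the no-drug effect in every row and recovers about half the gap. The two analyses also answer different questions, since the as-measured estimate includes the effect of added drugs by design.
- A reader might take it as fact that the rule removes the worst-controlled patients and differs by arm. The SAP states no prescribing rule, and blinded care providers limit differential prescribing. Patients already on a drug whose dose is raised stay in. Dependence on the marker is plausible but not documented, and lipids were not simulated.
- The loss of pre-start values matters only if pressure and lipids were measured at 6 months. The data collection figure is not shown, and the opening of section 7.4 leaves the time points open.
- Reading the exclusion as applying to starts after randomisation is an inference, though the natural one.

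All of this limits the size of the point. It does not remove the selection on a post-randomisation event, or the missing definition of a start.

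**Conclusion.** The point holds at low to moderate weight. For five secondary markers the concomitant-drug analysis compares groups that are no longer the randomised ones, and it may discard valid measurements. For systolic pressure, under the assumed inputs, the bias is about 0.2 to 0.4 mmHg at 12 months, well under one standard error, and up to about 1 mmHg at 6 months, roughly one standard error. No main conclusion changes. What changes is the weight that agreement with the main result can bear.

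The sizes rest on the assumed SD, correlation, drug effect and start rule, and on starts falling after the 6-month measurement. They should not be carried over to Apo B, triglycerides or HDL.

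**What to change.** In SAP section 7.4, for the five markers:

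1. Keep all randomised participants. Set only measurements taken after a drug start to missing, keep earlier ones, and fit the same mixed model. State that this targets a hypothetical estimand in which no such drug was started.
2. Define a start as one after randomisation, dated from the Pharmaceutical Information Network, which section 5.2.2 already uses for glucose-lowering drugs.
3. Tabulate starts by arm.
4. If the exclusion analysis is kept, label it a non-randomised comparison.

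The cost is SAP wording, drug dates for two more classes, and a few extra fits. The limits are that the method assumes starts are explained by recorded values, and that it gains nothing for participants who start before their first follow-up measurement. Adding an assumed drug effect back to post-start values is optional, because the SAP gives no effect sizes for it and a range would have to be assumed.

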Need for Antihyperglycemic Medication/Insulin Diet quality has significant impacts on glycemic control in the management of T2DM, including the need for antihyperglycemic medications and insulin use. Evidence indicates as diet quality improves, the need for medications/insulin can be de-intensified or discontinued altogether.⁶⁰ Data to assess this outcome will be extracted from the Pharmaceutical Information Network (PIN) database.⁶¹ Need for antihyperglycemic medication/insulin will be quantified by monitoring changes in medication/insulin 1) usage, defined as initiation or discontinuation, and 2) type including Metformin, Sulfonylureas, Repaglinide, DPP-4 inhibitors, GLP1 receptor agonists, SGLT2-inhibitors, Acarbose, Thiazolidinediones. Need for antihyperglycemic medication/insulin will be analyzed as an ordinal outcome.

We will use a novel scoring system that assigns points for each change based on its anticipated impact on A1C. Points will be attributed cumulatively for all qualifying changes during the program.

For an expected change in A1C of ~0.5%, 1 point will be assigned to the following changes.

- less than full dose of Metformin (<2000 mg/day) or Sulfonylureas (Gliclazide<60 mg/day, Glyburide <10 mg/day) or Repaglinide (<5 mg/day)
- any dose of DPP-4 inhibitor, SGLT2-inhibitor or Acarbose
- initiation of basal insulin

For an expected change in A1C of ~1%, 2 points will be assigned to the following changes.

- full dose of Metformin, Sulfonylureas or Repaglinide
- any dose of GLP1 receptor agonists or Thiazolidinedione
- initiation of bolus insulin

Addition of medication/insulin will be scored positively and reductions scored negatively to arrive at a final cumulative medication/insulin adjustment score for each participant. Deintensification will be considered a positive, and intensification will be considered a negative.

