Waist Circumference We will assess group differences in waist circumference as a continuous outcome using mixed-effects linear regression. Models will be adjusted for baseline waist circumference, and blocking variables (baseline A1C, gender, recruitment location). To improve the precision of effect estimates, models will also be adjusted for age, race/ethnicity, educational attainment, number of children living in the home, and diabetes duration. Additionally, all models will include baseline A1C data source (study measured vs administrative health data), and group (FoodRx vs comparison) indicator variables. We will include random intercepts for participants (participant study ID) to account for within-subject correlation due to repeated measures, and for primary care clinics (clinic study ID) to account for clustering of participants within clinics.

In addition to per-protocol and as-treated analyses, we will conduct sensitivity analyses for waist circumference to examine the impact of waist circumference as a binary outcome for men (circumference ≥ 102 cm/40 inches), and women (circumference ≥ 88 cm/35 inches) using mixed-effects logistic regression models.

Need for Antihyperglycemic Medication/Insulin We will assess group differences in need for antihyperglycemic medication/insulin as an ordinal outcome using mixed-effects logistic regression. Models will be adjusted for baseline need for antihyperglycemic medication/insulin, and blocking variables (baseline A1C, gender, recruitment location). Additionally, all models will include baseline A1C data source (study measured vs administrative health data), and group (FoodRx vs comparison) indicator variables. To improve the precision of effect estimates, models will also be adjusted for age, race/ethnicity, educational attainment, number of children living in the home, and diabetes duration. We will include random intercepts for participants

(participant study ID) to account for within-subject correlation due to repeated measures, and for primary care clinics (clinic study ID) to account for clustering of participants within clinics.

In addition to per-protocol and as-treated analyses, we will conduct sensitivity analyses for need for antihyperglycemic medication/insulin to examine the impact of excluding patients whose medication/insulin therapy remained unchanged during the 3 months prior to their program start date, throughout the program, and when participants taking insulin are excluded.

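### The medication/insulin sensitivity analysis excludes participants partly by whether their therapy changed during the program, which is the outcome being analysed

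*SAP*

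**What the plan says.** SAP section 5.2.2 (Clinical Health Markers) builds the outcome from therapy changes: "Need for antihyperglycemic medication/insulin will be quantified by monitoring changes in medication/insulin", by initiation or discontinuation and by type. The window is the program itself: "Points will be attributed cumulatively for all qualifying changes during the program". The sign rule is "Addition of medication/insulin will be scored positively and reductions scored negatively to arrive at a final cumulative medication/insulin adjustment score for each participant".

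Section 7.4 (Primary Manuscript) gives the main analysis: "We will assess group differences in need for antihyperglycemic medication/insulin as an ordinal outcome using mixed-effects logistic regression". Section 6.3 sets the population for all outcomes: "Analyses will be intention-to-treat using all available data for parameter estimation of primary, secondary, and exploratory outcomes".

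The sensitivity analysis in section 7.4 then examines the effect of "excluding patients whose medication/insulin therapy remained unchanged during the 3 months prior to their program start date, throughout the program", and also of excluding participants who take insulin. It gives no purpose for either exclusion and no date at which insulin use is judged.

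**The concern.** A participant whose therapy never changes during the program has an outcome score of 0. Excluding participants because their therapy did not change removes them on the value of the dependent variable, observed after randomisation.

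This matters here because section 4.3 leaves treatment to usual care, "including adjustments to medication regimes to improve glycemia at the providers discretion". If the incentive spares some participants an intensification they would otherwise have had, that benefit shows up as more unchanged participants in the FoodRx arm, and those are the people the rule removes. A result reported as a robustness check could then disagree with the main model, or agree with it too strongly, for reasons unrelated to robustness.

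The blood pressure and lipid sensitivity analyses in the same section are different. They exclude on starting a co-treatment, not on the outcome being modelled.

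**Working it through.** **The plan's own figure.** The SAP states no rate, sample size or power for the medication outcome, so there is nothing to reproduce. The check compares definitions and adds an illustration with assumed rates.

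**Step 1: the definitions side by side.**
- Outcome (5.2.2): signed sum of qualifying changes during the program. No change gives 0.
- Exclusion (7.4): therapy unchanged in the 3 months before the start and/or throughout the program.
- Two separate exclusions: the in-program one removes every participant with unchanged therapy.
- One joint condition (unchanged in both periods): it removes those unchanged during the program who were also stable beforehand. It still depends on the outcome.
- A slip for changed instead of unchanged: applied during the program, it would keep only participants scoring 0 and leave nothing to compare.

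**Step 2: separate reading, assumed rates.** Comparison group: 30% intensified, 10% deintensified, 60% unchanged. FoodRx: 15% intensified, with deintensification varied.

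Odds ratio for intensification in everyone: (0.15/0.85) / (0.30/0.70) = 0.176/0.429 = 0.41, whatever the deintensification rate.

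Among participants with any change, the comparison share intensified is 0.30/0.40 = 0.75, odds 3.

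| FoodRx deintensified | Share intensified among changers | Odds | Odds ratio among changers |
|---|---|---|---|
| 5% | 0.15/0.20 = 0.75 | 3 | 3/3 = 1.0 |
| 10% | 0.15/0.25 = 0.60 | 1.5 | 1.5/3 = 0.50 |
| 15% | 0.15/0.30 = 0.50 | 1 | 1/3 = 0.33 |

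**Step 3: the ordinal scale.** The SAP's model is ordinal, so I fitted a proportional-odds model by maximum likelihood to the same proportions in three categories (deintensified, unchanged, intensified). The common odds ratio in everyone is 0.63, 0.55 and 0.48 for the three rows. With the middle category removed, two categories remain and the ordinal odds ratio equals the last column: 1.0, 0.50 and 0.33. The effect is hidden, changed little, or exaggerated.

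**Step 4: joint reading, where only some unchanged participants are removed.** Assumed deintensified/unchanged/intensified: comparison 10/50/40%, FoodRx 7/65/28%.
- Everyone: (0.28/0.72) / (0.40/0.60) = 0.58.
- 50% of the unchanged removed: shares intensified 0.40/0.75 = 0.533 and 0.28/0.675 = 0.415; odds ratio 0.62.
- 80% removed: 0.40/0.60 = 0.667 and 0.28/0.48 = 0.583; odds ratio 0.70.
- All removed: 0.40/0.50 = 0.80 and 0.28/0.35 = 0.80; odds ratio 1.00.

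**Step 5: the opposite direction.** Comparison 10/50/40%, FoodRx 20/40/40%, so the arms differ only in deintensification. With scores of -1, 0 and 1, the mean difference in everyone is (0.40 - 0.20) - (0.40 - 0.10) = -0.10. Among changers it is 0.20/0.60 - 0.30/0.50 = -0.27. The odds ratio for intensification moves from 1.00 to (0.667/0.333) / (0.80/0.20) = 0.50.

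**Step 6: no effect.** With 10/50/40% in both arms, 80% of changers are intensified in each arm and the odds ratio stays 1.00.

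**The case against.** The strongest reply is that little rests on this. It is one sensitivity analysis of one secondary outcome, section 6.3 keeps the main model on all randomised participants, and section 6.5 presents secondary findings as exploratory. That stands and limits the weight of the point.

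Four stronger readings are tempting, and the SAP does not support them.

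- **That every participant with a score of 0 is removed.** The score is a signed sum. Someone who adds a 1-point drug and stops another 1-point drug scores 0, but their therapy changed, so they are kept. On the joint reading, so is anyone adjusted before the start and stable afterwards. The rule removes participants with unchanged therapy, which is not the same set.
- **That the exclusion manufactures an effect from nothing.** Step 6 shows that identical distributions give no difference. Step 5 shows a real difference in one direction of change being enlarged and appearing in another contrast.
- **That a real effect must vanish.** The odds ratio of exactly 1.0 arises when both directions of change are halved. Section 5.2.2 expects better diet to allow de-intensification. If deintensification rises to 15%, the effect looks larger among changers, not smaller.
- **That the pre-program part points the wrong way.** A check for unstable baseline therapy would exclude participants whose regimen changed beforehand, so the wording looks reversed. But the SAP states no purpose. It may intend a look at participants under active adjustment. One can ask for the purpose but not presume it.

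None of this rescues the in-program condition, which depends on the outcome under every reading.

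**Conclusion.** The concern holds for the in-program condition. By the SAP's own score definition, that condition selects participants on the post-randomisation outcome, so the comparison among those remaining is not a randomised one. This follows from the definitions and needs no assumed rates.

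The size does rest on assumptions, because the SAP gives no rates of medication change. Over the values tried, an intensification odds ratio of 0.41 in everyone becomes anything from 0.33 to 1.0 among changers. Partial exclusion under the joint reading moves 0.58 to 0.62 or 0.70. The direction cannot be known in advance.

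The point is minor in scope. The main intention-to-treat model for this outcome and the A1C analysis are untouched.

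**What to change.** Rewrite the sentence in section 7.4 as follows.

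1. Drop the in-program condition and keep participants with unchanged therapy in the model with score 0.
2. Define any therapy-stability restriction only from data before first randomisation. State its purpose and whether it removes participants with changed or with unchanged therapy. If it is a check for unstable baseline therapy, it should exclude those whose regimen changed before the start.
3. Define the insulin exclusion by use before first randomisation. Starting insulin during the program earns points in the outcome score, so an exclusion judged later would raise the same problem.
4. Fix the anchor date for the 31 restarted participants. Section 7 says the program ran 11 weeks and resumed 12 weeks later. A 3-month window counted back from the restart would lie mostly or wholly after their first randomisation.

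The cost is a sentence or two in the SAP. No new data are needed beyond the pharmacy records already planned, provided the extract reaches back 3 months before first randomisation.
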